6.2 Populations vulnerable to undue influence or coercion

Not applicable

7. Subject compensation

Participants will receive \$100 on a pre-paid debit card (Clincard) upon completion of the study.

8. Study procedures

8.1 Consent

Upon recruitment, potentially interested participants will be directed to the Way to Health internet research portal. Upon reaching the portal, eligibility will be determined based on their responses to screening questions.

The Way to Health portal will take eligible potential participants through an automated online informed consent session. The consent session will be divided into sections and potential participants will have to click a button to advance through each section. This is to help ensure that participants read the consent form thoroughly by breaking down the form into more manageable blocks of text. Successive screens will explain the voluntary nature of the study, the risks and benefits of participation, alternatives to participation, and that participants can cease to participate in the study at any time.

On the final consent screen, potential participants who click a clearly delineated button stating that they agree to participate in the study will be considered to have consented to enroll.

Following consent and the run-in period, the participant will be randomized to intervention or control arm by the web application. The participant will see a description of the details specific to that arm. Participants will be provided with details regarding how to contact the research team via email or phone at any time if they wish to withdraw from the study subsequently or have any questions or concerns about participation. Such contact information will remain present via the subjects Way to Health individual study website dashboard throughout the study. Participants will also be able to access a PDF of the consent form through the study Way to Health site.

Waiver or Alteration of Informed Consent*

Are you requesting a waiver of, or alteration to, the informed consent process? Please choose one of the following and provide justification where appropriate:

No Waiver Requested

Waiver or alteration of required elements of consent

Waiver of written documentation of informed consent: the only record linking the subject and the research would be the consent document and the principal risk would be potential harm resulting from a breach of confidentiality.

Waiver of written documentation of informed consent: the research presents no more than minimal risk of harm to subjects and involves no procedures for which written consent is normally required outside of the research context

Written Statement of Research*

Will subjects be provided a written statement of the research?

Yes

No

8.2 Procedures

Enrollment. Potential participants will complete a screening questionnaire through the Way to Health portal. If the participant successfully passes the screening questions, they can be consented to the study. After screening and consent, participants will complete a survey through the way to health platform to provide demographic information (Age, gender, race, ethnicity, income, education, self-report comorbidities/health conditions) as well as a shipping address for the Fitbit to be sent to. Participants will then receive a Fitbit activity tracker and instructions for setting up the tracker and the Fitbit app on their smartphone. After participants have successfully set up their activity tracker and app, and have linked their Fitbit account to the Way to Health website, they will begin the study run-in period.

Run-In Period. Eligible participants will be mailed a wearable activity tracker that captures data on daily steps counts and asked to use the device for two weeks to get accustomed to it. During this period, we will use a protocol from prior work to estimate a baseline step count using the second week of data. The first week of data will be ignored to diminish the tendency for use of devices in week 1 of receiving a new device to be significantly higher than what might be observed at steady state. To prevent risk of mismeasurement, we will ignore any daily values less than 1000 steps because evidence indicates these values are unlikely to represent capture of actual activity. Once baseline is established, participants will be contacted to conduct goal selection with a step goal of increase of 33%, 40%, 50% or choose a custom goal as long as it is at least 1500 steps greater than baseline. In prior work, we find that on average participants chose ambitious goals and more than half selected a 50% step increase.

Participants with an average of 7500 or greater steps per day during days 8 - 14 of run-in will be ineligible and will not be randomized into the study.

Randomization. After establishing baseline, participants will be randomly assigned to control or interventions using a 1:1 allocation and stratifying on baseline step count (< 4000, 4000-7000 steps, >7000 steps) using an electronic number generator through the WTH platform. All participants will be asked to use the wearable device during the day and at night to measure activity. Each participant will select whether he or she would like to primarily receive study communications by text message, e-mail, or automated interactive voice response phone call.

Cognition and Function Measures. Within 2 weeks of randomization (study weeks 2-4) and within 2 weeks after completing the intervention period (study weeks 15-16), participants will complete online survey-based assessments and virtual (video call) assessments of function (Timed Up and Go and 30-second Chair Stand) and cognition (Verbal Naming; Category Fluency; Trail Making; Number Span; Blind MOCA). The online surveys will be completed through the Way to Health online platform. Research staff will contact participants to schedule and conduct video calls to complete the tests of function and cognition.

Intervention Period.

Control: Participants in the control arm will receive a study device (e.g. FitBit) but no other interventions during the intervention or follow-up periods.

Intervention: Intervention participants will enter a game designed with behavioral economics (BE) concepts to address predictable barriers to behavior change during the 12-week intervention period. The components of the gamification intervention are described below:

Pre-commitment: Each participant signs a contract agreeing to try their best to achieve their daily step goal. Pre-commitment helps to motivate behavior change by increasing perceived accountability.^{18,19} Points: Each week, participants are endowed 70 points (10/day) prospectively rather than awarded after goal achievement to leverage the BE concept loss aversion that individuals are more motivated by immediate losses than gains.²⁰⁻²² Each day that the goal is not met, they are informed that they lost 10 points. Points are replenished at the start of the week to leverage the BE concept of the “fresh start effect” that individuals are more motivated for aspirational behavior around temporal landmarks such as the start of the week.⁵⁰ Levels: At the end of the week, if the participant has 40 points or more, he or she will advance one level. The levels include: blue (lowest), bronze, silver, gold, platinum (highest). If they have < 40 points, they drop down one level. This creates a sense of achievable goals (goal gradients)²³ and anticipated regret.²⁴⁻²⁷ Each participant begins in the middle (silver), so higher levels seem within reach and they will feel a sense of loss from dropping down a level. Support partner: Each participant will select a spouse, family member, or friend that they see often to serve as a sponsor and receive a weekly email participant’s progress including points, game level, and average step count. This supportive sponsor will help to enhance social incentives to motivate the individual towards his or her goal.¹³

Follow-Up Period. At the end of the 12 week Intervention Period participants will enter a 6 week Follow-Up Period during which interventions will cease but passive data collection of step counts will continue.

Exit Survey. Participants will complete an end-of-study questionnaire on their experience with the wearable device and intervention design. Participants will be asked to describe elements that helped them to achieve their physical activity goals (and elements that did not help) and suggestions on how to improve the design of the interventions.

Upon completion of the study, participants will receive payment of \$100 on a pre-paid debit card (Clincard).

8.3 Instruments

Step Count: Daily step count data will be uploaded daily from participants' activity trackers.

Screening Survey: A screening survey will be administered through the study website prior to enrollment to assess eligibility for the study. The survey will query age, use of smart phone, current activity level, participation in other research, ability to safely increase physical activity, availability of study partner, and knowledge of APOE genotype.

Baseline/demographics: After consent and confirmation of eligibility, participants will complete a survey through the way to health platform to provide demographic information (Age, gender, race, ethnicity, income, education, self-report comorbidities/health conditions) as well as a shipping address for the Fitbit to be sent to.

Cognition and Function: During the first two weeks of the intervention period and the first two weeks of the follow up period, participants will complete virtual (video call) assessments of function (Timed Up and Go and 30-second Chair Stand) and cognition (Verbal Naming; Category Fluency; Trail Making; Number Span; Blind MOCA). Research staff will contact participants to schedule and conduct video calls to complete the tests of function and cognition.

Exit survey: Participants will complete an end-of-study questionnaire on their experience with the wearable device and intervention design. Participants will be asked to describe elements that helped them to achieve their physical activity goals (and elements that did not help) and suggestions on how to improve the design of the interventions.

9. Analysis plan

Similar to our prior work,^{22,44,54} the primary analysis will fit mixed effect regression models to evaluate changes in physical activity (steps per day and minutes of MVPA) adjusting for each participant's baseline measure, time using calendar month fixed effects, participant random effects, and accounting for repeated measures. Secondary analyses will fit a fully adjusted model including other variables of interest such as participant demographic characteristics and comorbidities. We will also conduct a-priori exploratory subgroup analyses for participants with elevated risk (APOE4 carriers) and higher levels of social support on 1o and 2o outcomes. For these outcomes, we estimate a standard deviation of 2500 steps and a sample of 100 participants allocated in a 1:1 distribution (50 in each arm), will ensure at least 80% power to detect a 1000 step difference. This calculation assumes a 10% dropout rate and a conservative Bonferroni adjustment of the type I error rate with a 2-sided alpha of 0.017.

In exploratory analyses, we will compare results from virtual functional and cognitive tests at the beginning of the study (after randomization) with results during the follow up period (after intervention ends). We do not anticipate major changes in these measures and are not powered to detect minor changes – these are feasibility measures to demonstrate we can conduct virtual performance tests at multiple intervals only.

We will also conduct exploratory subgroup analyses of factors that may influence our primary outcome (change in mean steps/day) such as participant-reported social support and neighborhood walkability as determined by address/zipcode. These are factors that have been associated with steps in our prior work but this pilot will not adequately powered to detect statistical significance (we will explore for trends only).

10. Investigators

[name], MHS, MA is the Principal Investigator (PI). He is the Director of Penn Center for Evidence-based Practice; his research focuses on outcomes of hospitalization for older, vulnerable adults during transitions of care and mobile technologies to engage this population.

[name] is Co-Director of the Penn Memory Center and Director of the Penn Program on Precision Medicine for the Brain (P3MB). His research focuses on quality of life and ethical issues of disclosure of gene and biomarkers of Alzheimer's disease risk in older adults.

11. Human research protection

11.1 Data confidentiality

Paper-based records will be kept in a secure location and only be accessible to personnel involved in the study. Computer-based files will only be made available to personnel involved in the study through the use of access privileges and passwords. Wherever feasible, identifiers will be removed from study-related information. Precautions are in place to ensure the data are secure by using passwords and encryption, because the research involves web-based surveys.

11.2. Data Management

The Way to Health web platform will serve as the core mechanism for recruiting and enrolling subjects, transmitting general and intervention-specific messages, collecting activity tracker and online survey data, and providing regular feedback to subjects on their progress in the study.

The Penn Medicine Academic Computing Services (PMACS) will be the hub for the hardware and database infrastructure that will support the project and is where the Way to Health web portal is based. The PMACS is a joint effort of the University of Pennsylvania's Abramson Cancer Center, the Cardiovascular Institute, the Department of Pathology, and the Leonard Davis Institute. The PMACS provides a secure computing environment for a large volume of highly sensitive data, including clinical, genetic, socioeconomic, and financial information. Among the IT projects currently managed by PMACS are: (1) the capture and organization of complex, longitudinal clinical data via web and clinical applications portals from cancer patients enrolled in clinical trials; (2) the integration of genetic array databases and clinical data obtained from patients with cardiovascular disease; (3) computational biology and cytometry database management and analyses; (4) economic and health policy research using Medicare claims from over 40 million Medicare beneficiaries. PMACS requires all users of data or applications on PMACS servers to complete a PMACS-hosted cybersecurity awareness course annually, which stresses federal data security policies under data use agreements with the university. The curriculum includes Health Insurance Portability and Accountability Act (HIPAA) training and covers secure data transfer, passwords, computer security habits and knowledge of what constitutes misuse or inappropriate use of the server. We will implement multiple, redundant protective measures to guarantee the privacy and security of the participant data. All

investigators and research staff with direct access to the identifiable data will be required to undergo annual responsible conduct of research, cybersecurity, and HIPAA certification in accordance with University of Pennsylvania regulations.

Data will be entered into the database through several different mechanisms. Participants will enter their own personal information and respond to surveys through a PHP-based web interface. Activity tracker data will be transmitted from the activity tracker company to the study server through a secure connection. Researchers will have a separate interface that will allow them to manually enter data if needed. For example, to enter data from virtual cognitive and functional tests, researchers will login to Way to Health and complete evaluation forms based on attachments for Timed Up and Go (TUG), 30-second Chair Stand Test (30s CST), Verbal Naming, Category Fluency, Trail Making, Number Span, and Blind MOCA.

Wherever possible, data will be de-identified for analysis. Personal information and research data will be stored in separate SQL tables and will be linked by a computer-generated ID number.

It is unlikely that anyone will need to make corrections to the data, as most of the information is submitted by participants. Furthermore, the web platform will be set up with pre-specified ranges of eligible values for each question to minimize data entry errors. Specifically designated administrators will have the ability to make corrections, however each modification will be logged along with justification for the change. The original data will be preserved in a separate non-modifiable database.

11.3 Subject confidentiality

Research material will be obtained from participant surveys, assessments and from the wearable devices. All participants will provide informed consent for access to these materials. The data to be collected include demographic data (e.g., age, sex, self-identified race), outcome data, and daily activity data collected by the wearable device. Research material that is obtained will be used for research purposes only. The same procedure used for the analysis of automated data sources to ensure protection of patient information will be used for the survey data, in that identifiers will be used only for linkage purposes or to contact participants. The study identification number will be used on all data collection instruments. All study staff will be reminded to appreciate the confidential nature of the data collected and contained in these databases.

Data will be stored, managed, and analyzed on a secure, encrypted server behind the University of Pennsylvania Health System (UPHS) firewall. All study personnel that will use this data are listed on the IRB application and have completed training in HIPAA standards and the CITI human subjects research. Data access will be password protected. Whenever possible, data will be de-identified for analysis.

11.4 Subject privacy

Potential participants will have the option to accept or decline the study invitation. If participants accept, they acknowledge that their information will be shared with the study team and that a member of the study team will contact them. Those who decline the invitation will not be contacted again, and none of their information will be shared with the study team. Enrollment will include a description of the voluntary nature of participation, the study procedures, risks and potential benefits in detail. Potential participants will have the opportunity to ask questions and review the consent form information with family prior to making a decision to participate. Participants will be told that they do not have to answer any questions if they do not wish and can drop out of the study at any time. They will be told that they may or may not benefit directly from the study and that all information will be kept strictly confidential, except as required by law. All efforts will be made by study staff to ensure subject privacy.

11.5 Data disclosure

The following entities, besides the members of the research team, may receive data for this research study: -Fitbit, the company that designs and manufactures the wearable devices used in the study to track participant physical activity. RedCap, a secure web application where participants' informed consent forms will be stored. -Twilio, Inc., the company which processes some study-related messages. Twilio will store patients' phone numbers on their secure computers. -Qualtrics, Inc., the company which processes most study-related surveys. Qualtrics will house de-identified answers to these surveys on their secure servers. -The Office of Human Research Protections at the University of Pennsylvania -Federal and state agencies (for example, the Department of Health and Human Services, the National Institutes of Health, and/or the Office for Human Research Protections), or other domestic or foreign government bodies if required by law and/or necessary for oversight purposes.

11.6 Data safety and monitoring

At the time of enrollment, all patients will be given anticipatory guidance on when to seek medical attention (e.g. when to call their doctor should they feel dizzy, short of breath, chest pain, lightheaded, unstable, or otherwise unwell while ambulating). In addition, participants will be asked to report to the study team any episodes of these symptoms that occur during ambulation to research staff. Participants will also be reminded that they can always contact the study team by phone or email at any time (contact information will be given at the beginning of the study and will also be posted on the Way to Health platform, which can be accessed at any time by the participant). If any concerns of a participant event are identified, the study coordinator will reach out to the participant and complete the event reporting form. This form will be reviewed with the study PI to determine if any action is needed and if the participant can continue safely in the study. Any identified adverse events will be reported to the Institutional Review Board.

A Safety Officer will also be appointed to review IRB protocol and will review adverse events when enrollment is halfway complete. All adverse events that are serious or unexpected (i.e., have not been previously reported for the study's intervention) including death or hospitalization of a participant, will be reported to the IRB, Safety Officer, and NIA Program Officer within 24 hours of the PI's knowledge of the SAE.

[name] as the study principal investigator will be responsible for monitoring participant safety, data quality/confidentiality, and evaluating the progress of the study on a daily basis in conjunction with study staff. An NIA-approved SO will have the role/responsibility of reviewing the entire IRB-approved study protocol regarding subject safety and analysis, the informed consent document regarding applicability and readability, and participant recruitment and retention milestones. At the time of interim analysis (50% enrollment), the study team will prepare a safety report to be reviewed by the SO.

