11.7 Risk/benefit

11.7.1 Potential study risks

There are minimal risks to participants in this study. The potential risks to study participants include: breach of confidentiality and privacy as information about each participant including their physical activity and health will be recorded; the possibility that answering certain questions may make the participant feel slightly uncomfortable; excessive physical activity could lead to muscle soreness or injury; some skin irritation or rash from wearing the Fitbit watch, although this occurs rarely; increased in physical activity (walking) may increase the risk of falling, although this is also very rare.

We will minimize this risk of confidentiality breach by linking individual identifying information with participant ID numbers only in one single secure file that will only be accessed by the study team in the case of an adverse medical event, participant dropout, or if otherwise deemed necessary by the Principal Investigator. All other identifying information will be discarded after initial contact with the Study Coordinator. All other members of the research team will be able to view only participant ID numbers.

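### Adverse event capture relies on unsolicited reports, and the request made to participants does not name the falls, injuries and skin reactions that the protocol lists as risks

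*Combined protocol and SAP*

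**What the plan says.** Section 11.6 is the only part of the protocol that describes how adverse events are found. It begins: "At the time of enrollment, all patients will be given anticipatory guidance on when to seek medical attention". The example given is "when to call their doctor should they feel dizzy, short of breath, chest pain, lightheaded, unstable, or otherwise unwell while ambulating". The request to participants then refers back to that list: "participants will be asked to report to the study team any episodes of these symptoms that occur during ambulation to research staff".

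Two wider provisions follow. One is an open route: "Participants will also be reminded that they can always contact the study team by phone or email at any time". The other is a follow-up step: "If any concerns of a participant event are identified, the study coordinator will reach out to the participant and complete the event reporting form". Identified adverse events go to the IRB. Serious or unexpected events, with death and hospitalisation given as instances, go to the IRB, the Safety Officer and the funder's programme officer within 24 hours of the principal investigator learning of them. The Safety Officer reviews a safety report at 50% enrolment.

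Section 11.7.1 sets out the physical risks. It says "excessive physical activity could lead to muscle soreness or injury", mentions skin reactions to the watch, and says that more walking "may increase the risk of falling, although this is also very rare".

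Section 8.2 describes staff video calls and online surveys for all participants shortly after randomisation and again at study weeks 15-16, and an exit survey. No safety item is described for any of them. Section 9 plans no tabulation of adverse events by arm.

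**The concern.** The list that participants are asked to report from and the list of risks that the protocol expects are different lists. Someone who follows the request literally will report dizziness on a walk. The same person may not think to report a trip with no preceding symptom, a sore knee the next morning, or a rash under the strap. Everything else in 11.6 starts once a concern has been identified, and no schedule or method for identifying one is given.

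At stake is how the safety counts can be read. A low count of falls or injuries could mean that they were rare or that they were not mentioned, and the plan offers no way to tell the two apart. This bears on the Safety Officer's report and on any later statement that the programme was safe for adults aged 55-75 who are asked to walk more.

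**Working it through.** The documents state no adverse event rate and no expected reporting rate, so there is no figure to reproduce. The check is mainly a comparison of text.

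**Step 1. Named risks against the request.**

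| Risk in 11.7.1 | Named in the 11.6 request? | Nearest item in the request |
|---|---|---|
| Falls | No | Feeling unstable; overlaps in part, but a trip without warning need not fit |
| Muscle soreness or injury | No | Feeling otherwise unwell; tied to walking, while soreness may come later |
| Skin reaction to the device | No | None; not an event of walking |

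**Step 2. Is anyone asked on a schedule?** Sections 8.2, 8.3, 9, 11.2 and 11.6 describe no adverse event question, checklist or look-back period in either arm. The contacts where one could be placed already exist in both arms: the week 15-16 online survey and video call, and the exit survey.

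**Step 3. When would the information be used?** Section 5.1 counts a participant as enrolled once randomised. Section 5.4 sets the target at 100, allocated 1:1. Half of 100 is 50, or about 25 per arm. A participant reaches week 15 only after the 2-week run-in and the 12-week intervention (2 + 12 = 14 weeks), so many may not have got there at the 50% review. The pace of accrual is not stated.

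**Step 4. Illustration of under-reporting (assumed reporting shares).** If no event is reported among n participants, the one-sided 95% upper limit on the risk of a reported event is 1 - 0.05^(1/n). If a share s of events is reported, the limit on the true risk is that value divided by s.

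| n in the intervention arm | s = 1 | s = 0.8 | s = 0.5 |
|---|---|---|---|
| 25 (50% review) | 11.3% | 14.1% | 22.6% |
| 50 (full arm) | 5.8% | 7.3% | 11.6% |

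**Step 5. Illustration of unequal reporting (assumed risks and shares).** Expected reports = 50 x true risk x share reported.
- Same true risk of 10%, reporting 80% v 40%: 50 x 0.10 x 0.80 = 4 against 50 x 0.10 x 0.40 = 2, a false doubling.
- True risk 10% in the intervention arm and 5% in control, reporting 40% v 80%: 50 x 0.10 x 0.40 = 2 against 50 x 0.05 x 0.80 = 2, so a true doubling disappears.
- Equal reporting in both arms leaves the ratio unbiased.

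The first two results follow directly from the assumed shares. They show that an error could go either way, not that one is expected.

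**The case against.** A reader might infer that adverse events come only from symptoms felt while walking, and that falls and injuries are left out. The documents do not support that. The open contact route is not limited to symptoms or to walking, the event form applies to any identified concern, serious events are reportable whatever the activity, and the symptom list is introduced as an example. This objection stands: a fall can be recorded if it is volunteered. What remains is that nobody is prompted to volunteer it.

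A reader might also infer that reporting will differ by arm, because intervention participants are messaged about missed goals while controls receive the device "but no other interventions during the intervention or follow-up periods". The documents do not establish this either. The guidance, the request and the contact route are the same for everyone. The partner emails go to the partner, the game messages are not described as asking about safety, and an absence of other interventions is not an absence of contact. A difference is possible, but its direction and size are unknown.

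Three further objections have force. The trial is a pilot that the protocol judges to be of minimal risk, and no planned analysis compares adverse events by arm. With about 25 per arm the 50% review is imprecise even with perfect capture: the limit is already 11.3% under complete reporting. And the consent pages and the wording of the surveys are not available here, so they may contain prompts that the protocol text does not describe. These points keep the matter small. They do not remove the mismatch between 11.6 and 11.7.1.

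**Conclusion.** The point holds in a limited form. The request in 11.6 does not name the physical harms that 11.7.1 lists, and no scheduled safety question is described for either arm. Falls, injuries and skin reactions are therefore unprompted, though not excluded. Under-reporting is likely; that is a judgement from the passive design, not a figure in the documents.

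Its size cannot be derived from the plan. The limits in the illustration rest on assumed reporting shares and show only that passive counts would give weaker reassurance than they appear to. No bias between arms is shown. The primary and secondary step-count analyses are unaffected. This is an inexpensive improvement, not a flaw that threatens the trial.

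**What to change.** 1. In 11.6, add falls, injuries (including muscle soreness) and device skin reactions to the reporting request, whether or not they occur while walking. This part acts from enrolment, so it is the one that can inform the Safety Officer's review at 50%.
2. Put the same short yes/no items on falls, injury, skin reaction and hospitalisation to both arms in the planned week 15-16 survey or video call and in the exit survey. These will come too late for many participants at the 50% review, but they give complete and comparable information at the end.
3. In section 9, state that the answers to these items will be tabulated by arm, separately from spontaneous reports.

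If the consent form or the surveys already contain such items, a cross-reference in 11.6 is enough.

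The cost is a sentence in 11.6, a line in section 9 and a few survey items. Surveys become slightly longer and staff will log more minor events. No new visit or staff is needed.
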